2.2 BACKGROUND

Dialysis patients experience high end-of-life treatment intensity that may not reflect their wishes. Despite advances in dialysis, adjusted all-cause mortality rates are 6-8 times greater for dialysis patients than for individuals in the general age-matched Medicare population.¹ Only 50% of dialysis patients are alive 3 years after the onset of ESRD.¹ End-of-life treatment intensity in this population is also substantially greater than that reported for other Medicare beneficiaries with life-limiting illnesses.²¹ For instance, in a study of older Medicare beneficiaries (≥ 65 years; $N=100,000$) those on dialysis experienced significantly higher rates of hospitalization (76% vs 61% in cancer), ICU admission (48.9% vs 29% in cancer), and use of intensive procedures (29% vs 9% in cancer) during the final month of life.²²

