Dialysis patients and their surrogates are not knowledgeable about the natural course of ESRD. Although withdrawal of dialysis precedes 1 in 4 deaths of patients with ESRD,²³ withdrawal from dialysis and aggressive treatment is very rarely (< 6%) discussed by patients and their surrogates with sufficient time to consider alternatives such as hospice or dying at home.²³⁻²⁶ In a study of over 530 chronic dialysis patients, only 19% indicated that they would want to continue dialysis if severely cognitively or functionally impaired, and 65% stated that they prefer to die at home or in hospice rather than in a hospital.²⁷ Patients' preferences for end of life care are significantly influenced by the patients' illness representations (e.g., perceived illness severity).²⁸ That is, when patients understand their illness severity and progression, they are likely to forgo futile end-of-life treatment, such as mechanical ventilation and CPR. In our work we have discovered that because so many dialysis patients are unaware that they are likely to die from an acute illness or complication (e.g., stroke, infection) rather than die from ESRD per se, they endorse the notion that with dialysis they can live as long as those without ESRD.^{18,29} Similarly, surrogates are equally unaware of patients' likely illness progression and comorbidities; surrogates report that prior to the time of end-of-life decision making they have not been told that the patient's illness cannot be cured.⁹ Studies indicate that spouses' judgments about dialysis patients' preferences for continuation of dialysis were only modestly correlated with patients' preferences ($r = .33$),^{30,31} and spouses do not have intimate knowledge of whether or how long the patient would want to pursue life-sustaining measures.^{32,33} Our previous work demonstrated that surrogates are overly confident about their ability to act as a surrogate in that they have little understanding of the patient's preferences and yet report confidence in understanding the patient's wishes and their role as a surrogate.³⁴

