4 STUDY DESIGN**4.1 OVERALL DESIGN**

We will conduct a dialysis clinic-level cluster randomized trial with two groups, SPIRIT versus usual care followed by delayed SPIRIT. We will recruit 400 dyads of patients on chronic (“prevalent”) dialysis who are at high risk of death in the next year and their surrogate decision-makers (total 800 individuals) from 30 free-standing dialysis clinics in 4 states. The primary outcomes are patient and surrogate self-report preparedness for end-of-life decision making. The implementation evaluation data will be obtained throughout the study course. Upon patient death (anticipate 20% of patients; n = ~ 80), we will assess surrogates’ post-bereavement distress. Patient participation will end at 9 months (to allow for obtaining Medicare claims data during the study period) or death, whichever occurs first; surrogate participation will end at 9 months or at the completion of 3-month post-death follow-up. If patient is still living at 9 months, we will ask for an extension of follow up period to include 12 more months. Medicare claims data for end-of-life treatment intensity will be obtained quarterly. Clinics assigned to usual care will receive the delayed implementation, SPIRIT, in Year 4, Q1. This is a Phase III trial of an intervention that involves minimal risks and has proven to be efficacious, and thus no interim analysis is planned.

For Supplement Aims:

We will use a randomized controlled trial design with two groups: SPIRIT-dementia and usual care. From the pool of screened but excluded ESRD patients, we will recruit 30 dyads of patients with mild to moderate dementia and their surrogates. The groups will be stratified by race (white vs non-white). Patient and surrogate self-reported preparedness for end-of-life decision making will be measured at baseline and shortly after the intervention (by phone in the next 2-3 days) as done in the pilot test of SPIRIT-dementia. Additionally, we will review the patient's medical record to examine care decisions at 6 months or after the patient's death, whichever occurs first. In the case of patient death, we will also assess surrogates' post-bereavement outcomes (anxiety and depression symptoms) at 1 month after the patient's death. Based on previous research,¹³ we anticipate about 50% of the supplement sample will die within 12 months of enrollment. All data collection from study participants will be telephone-based.

Supplement cohort study:

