5 STUDY POPULATION

5.1 INCLUSION CRITERIA

Patient eligibility criteria:

- a) 18 years or older
- b) on either hemodialysis or peritoneal dialysis
- c) able to understand and speak English.

Surrogate eligibility criteria:

- a) 18 years or older (to serve as a surrogate decision-maker, the individual must be an adult)
- b) being chosen by the patient.

Roughly 76 providers at the 29 clinics, including all medical directors, nurse managers, social workers, and those who are selected to conduct SPIRIT sessions will participate in the implementation evaluation.

For Supplement Aims:

Patient eligibility criteria:

- a) Receiving in-center hemodialysis at Emory or UVA dialysis clinics.
- b) Diagnosed with dementia of any etiology (or those for whom their care providers, either MD or APRN, are suspicious of dementia) with having mild to moderate cognitive impairment based on a Montreal Cognitive Assessment (MoCA) score of 13 or higher,^{54,55} or a Saint Louis University Mental Status (SLUMS) score of 21 or higher (high school education) or 20 or higher (less than high school education)⁵⁶
- c) Able to understand and speak English
- d) A UBACC (decision-making capacity screening test) score ≥ 11 . Because dementia is largely under-diagnosed in the clinical setting for patients with ESRD, to identify additional patients with possible dementia, a trained research assistant will administer the MoCA or SLUMS to patients who are suspected (by dialysis clinicians) of having dementia. MoCA or SLUMS will take about 10 minutes to complete.

Surrogate eligibility criteria:

- a) 18 years or older (to serve as a surrogate decision-maker, the individual must be an adult)
- b) being chosen by the patient.

For supplement cohort study:

Dyads who completed the parent study's baseline (T1) and 2-week follow-up (T2) before March 13, 2020.

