We will link study data to publicly available USRDS data. The USRDS captures inpatient and outpatient Medicare claims on all treated U.S. ESRD patients and releases these data annually free of charge. Medicare claims data are the most complete and reliable source of data on end-of-life care intensity because patients on dialysis are Medicare beneficiaries. The USRDS data are far superior to that which could be obtained through individual hospitals because data collection at the latter is extremely difficult and highly likely to result in missing data. From the inpatient and outpatient claims data, we will obtain dates and attributed causes of death; dates of hospital, skilled nursing facility, and hospice admissions and discharges; dates of outpatient encounters (including dialysis sessions and ED visits); and diagnostic and procedure codes for all inpatient and outpatient encounters. Thus, we will be able to determine hospitalization, ICU days, days hospitalized, use of intensive procedure, (dis)continuation of dialysis (also from CMS Form 2746), and hospice use during the final month of life. We will consider the following to be intensive procedures: mechanical ventilation, feeding tube placement, dialysis, and cardiopulmonary resuscitation.²² These intensive procedures will be identified using HCPCS and ICD-9-CM codes (e.g., ICD-9 codes for intubation and mechanical ventilation: 96.04, 96.05, 96.7X).⁸³

Descriptors and Potential Covariates

- Patients and surrogates will complete a **Sociodemographic Profile** which includes age, gender, race and ethnicity, type of relationship between patient and surrogate, marital status, religious affiliation, education, household income, previous end-of-life decision-making experience, and previous participation in an ACP discussion or AD completion.
- To describe the sample, **the patient's clinical characteristics**, including dialysis modality, years on dialysis, comorbid conditions will be abstracted from the patient's EMR.
- **Care providers' sociodemographic data** will include age, gender, race and ethnicity, education, and years of practice.
- At baseline, we will collect **clinic-level contextual data**⁸⁴ that could facilitate understanding study results, including staffing, patient census, rural-urban status,⁸⁵⁻⁸⁹ palliative care and hospice availability, and proximity of hospitals.

For Supplement Aims,

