9 STATISTICAL CONSIDERATIONS

9.1 STATISTICAL HYPOTHESES

- Primary Endpoint(s):
 - 1) The number of SPIRIT dyads who are congruent on goals of care at 2 weeks post-intervention will be significantly higher than that of control dyads.
 - 2) Patient decisional conflict scores at 2 weeks post-intervention will be significantly lower than those of control dyads.
 - 3) Surrogate decision making confidence (DMC) scores at 2 weeks post-intervention will be significantly higher than those of control dyads.

- 4) The number of SPIRIT dyads who are congruent on goals of care and confident surrogate (DMC=3 or higher) at 2 weeks post-intervention will be significantly higher than that of control dyads.
- Secondary Endpoint(s):
 - 1) HAD-anxiety scores in SPIRIT surrogates will be significantly lower than those of control surrogates at 3 months after the patient's death.
 - 2) HAD-depression scores in SPIRIT surrogates will be significantly lower than those of control surrogates at 3 months after the patient's death.
 - 3) PTSS-10 scores in SPIRIT surrogates will be significantly lower than those of control surrogates at 3 months after the patient's death.
- Exploratory: Among patients who have died,
 - 1) The percentage of patients hospitalized during the final month of life in the SPIRIT group will be significantly lower than that in the control group.
 - 2) The percentage of patients admitted to an ICU during the final month of life in the SPIRIT group will be significantly lower than that in the control group.
 - 3) The percentage of patients having intensive procedures during the final month of life in the SPIRIT group will be significantly lower than that in the control group.
 - 4) The length of hospital stay during the final month of life in the SPIRIT group will be significantly shorter than that in the control group.

For Supplement Aims:

- Aim 1:
 - 1) The number of SPIRIT dyads who are congruent on goals of care at 2-3 days post-intervention will be higher than that of control dyads.
 - 2) Patient decisional conflict scores at 2-3 days post-intervention will be lower than those of control dyads.
 - 3) Surrogate decision-making confidence (DMC) scores at 2-3 days post-intervention will be higher than those of control dyads.
 - 4) The number of SPIRIT dyads who are congruent on goals of care and confident surrogate (DMC=3 or higher) at 2-3 days post-intervention will be significantly higher than that of control dyads.

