9.4.9 EXPLORATORY ANALYSES

SPIRIT effectiveness on end-of-life treatment intensity: Among patients who die during the initial SPIRIT implementation and follow-up, percentages of patients hospitalized, having ICU admission, having intensive procedures and length of hospital stay in the final month of life will be summarized using descriptive statistics, 95% CIs, and graphical displays. The exploratory examination of SPIRIT's effectiveness on improving these outcomes, we will use the same analytic approach as in the analysis of the primary endpoints (See 9.4.2).

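### The exploratory intensive-procedures endpoint counts routine maintenance dialysis, so as written it sits at about 75–100% and barely registers ventilation, feeding tubes or CPR

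*Combined protocol and SAP*

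**What the plan says.** Section 8.1 defines the endpoint: "We will consider the following to be intensive procedures: mechanical ventilation, feeding tube placement, dialysis, and cardiopulmonary resuscitation". The definition cites reference 22. Procedures are to be identified by HCPCS and ICD-9-CM codes, but the only codes given, as examples, are for intubation and ventilation. The claims extract covers "dates of outpatient encounters (including dialysis sessions and ED visits); and diagnostic and procedure codes for all inpatient and outpatient encounters". The same paragraph derives continuation or discontinuation of dialysis as a separate item, from claims and CMS Form 2746.

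Section 5.1 requires every parent-trial patient to be "on either hemodialysis or peritoneal dialysis". Section 2.2 states that "withdrawal of dialysis precedes 1 in 4 deaths of patients with ESRD" and, for older dialysis patients, reports "use of intensive procedures (29% vs 9% in cancer) during the final month of life", again citing reference 22.

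Exploratory hypothesis 3 in section 9.1 reads: "The percentage of patients having intensive procedures during the final month of life in the SPIRIT group will be significantly lower" than in the control group. Section 9.4.9 plans percentages with 95% confidence intervals and then says "we will use the same analytic approach as in the analysis of the primary endpoints", which means the mixed logit model of section 9.4.2. The synopsis, the objectives table in section 3, and sections 9.1 and 9.4.9 all use the endpoint; none narrows the word dialysis.

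**The concern.** In a general population, dialysis in the last month of life marks intensive treatment. Here it is the condition of entry. Taken literally, the definition makes nearly every decedent positive because of routine care, so the composite says little about the three procedures that would mark escalation.

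Three things follow. A real reduction in ventilation, feeding tubes or CPR would be almost invisible, and a null result could be reported as no reduction in intensive procedures. Any movement would mainly reflect dialysis stopped more than a month before death, a different construct that section 8.1 already captures on its own. And a logit model with a random intercept, random slope and interactions could be fitted to an outcome with only a handful of negatives, where it may not be estimable.

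**Working it through.** The documents give no expected rate, effect or power for this endpoint, so there is no planned figure to reproduce. The only stated rate is the 29% in section 2.2.

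**Inputs from the documents**
- Share of deaths preceded by dialysis withdrawal: w = 0.25 (section 2.2).
- Deaths: about 80 (section 4.1, "anticipate 20% of patients" of 400) or about 160 (section 8.1, 40% of 400). The two sections disagree, so both are used: 40 or 80 per arm.
- Clusters: 19 (power table, section 9.2) or 4 + 3 + 8 + 5 + 8 = 28 (section 6.3). ICC 0.01–0.04 (section 9.2).

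**Assumptions**
- q, the share of withdrawals made more than a month before death. The documents give no timing, so q runs from 0 to 1.
- Rate of the other three procedures: p = 0.29, borrowed from section 2.2. That figure is for patients aged 65 or older; the trial enrols from 18.
- Early withdrawers have a rate p_w of the other procedures between 0 and 0.29.
- Claims capture all dialysis, and patients leave dialysis only by withdrawal.

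**Rate of the endpoint as written.** A negative needs early withdrawal and none of the other procedures:

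rate = 1 − w·q·(1 − p_w)

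| q | Expected rate | Expected negatives, 80 deaths | Expected negatives, 160 deaths |
|---|---|---|---|
| 0 | 100% | 0 | 0 |
| 0.05 | 98.8–99.1% | about 1 | 1–2 |
| 0.25 | 93.8–95.6% | 4–5 | 7–10 |
| 1 | 75.0–82.3% | 14–20 | 28–40 |

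Negatives are for both arms together, with no treatment effect. For the composite to be as low as 29%, at least 71% of decedents would need no dialysis claim in the final month, against 25% who withdraw at any time.

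**Dilution.** Assume SPIRIT has an odds ratio of 0.5 on the other procedures:
- control odds = 0.29/0.71 = 0.408
- SPIRIT odds = 0.204, so the rate is 0.204/1.204 = 17.0%
- difference = 12.04 points

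With p_w equal to the arm's rate of other procedures, the composite difference is w·q × 12.04 points. This is the upper end; if early withdrawers have none of the other procedures (p_w = 0), the difference is zero.

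| q | Composite difference (at most) | Power, 40–80 deaths per arm |
|---|---|---|
| 0.05 | 0.15 points | 0.001–0.007 |
| 0.25 | 0.75 points | 0.044–0.047 |
| 1 | 3.0 points | 0.065–0.077 |

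Power is for the two-sided 5% pooled z-test, by exact binomial enumeration, ignoring clustering.

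**With maintenance dialysis excluded.** For 29% versus 17%, power by the normal approximation is 0.25 (40 per arm) and 0.44 (80 per arm). With design effect 1 + (m − 1)·ICC, where m is deaths per cluster, it is 0.22–0.24 and 0.35–0.42.

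**What can move the composite.** If SPIRIT doubled early withdrawal, power for the composite as written would be about 0.13–0.27 at q = 0.25 and 0.44–0.91 at q = 1. The endpoint responds to stopping dialysis early, not to the other procedures.

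**The case against.** The strongest reply is that this is an undefined term, not a demonstrated ceiling. The 29% comes from dialysis patients in the same source as the definition, so that source presumably did not count maintenance sessions. The codes shown are only examples, and dialysis discontinuation is listed as a separate item. All this suggests a narrower meaning was intended. That may be so, but no narrower meaning is written, and a programmer who follows section 8.1 would count maintenance sessions.

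A second reply is that continued dialysis belongs in the construct, because the Goals-of-Care Tool treats dialysis as life-sustaining treatment. That is a fair reason to report it. It does not justify merging it with three rarer events that it swamps.

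Several smaller points stand:
- Using 29% as the rate of the other procedures is an assumption. A lower rate would shrink both the undiluted and the diluted difference; the ceiling would remain.
- Incomplete claims capture would let some dialysed patients appear negative. And 75% is not a hard floor in the SPIRIT arm, where withdrawal could exceed 1 in 4.
- Non-estimability of the model is a risk, not shown, and is weaker near q = 1.
- Section 9.4.9 starts with descriptive summaries. But a percentage near 100% driven by routine care misleads whether or not it is tested.
- The amendment history (section 10.2, version 7) reports deaths below 4% of recruits at that time, so numbers may be smaller than either planning figure.

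**Conclusion.** The concern holds. Followed as written, section 8.1 produces an endpoint at roughly 75–100%, in conflict with the 29% in section 2.2. At most a quarter of any effect on ventilation, feeding tubes and CPR passes through to it, and much less if most withdrawals occur in the final month.

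The range rests on the 1-in-4 withdrawal figure applying to trial decedents, near-complete claims capture, and the unknown timing parameter q. The conclusion holds across the whole range of q. The power figures also depend on an assumed odds ratio of 0.5 and the borrowed 29%.

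The scope is limited to one of four exploratory Aim 4 outcomes. Correcting the definition makes the endpoint interpretable but does not make it well powered: 0.22–0.42 after clustering, under the same assumptions. The plan should be changed before claims are extracted.

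**What to change.** In section 8.1:
- State that maintenance dialysis does not count toward the intensive-procedure composite. If some other form of dialysis is meant, name it and list its codes.
- Give the full code list for every component, not only intubation and ventilation.
- Report continuation or discontinuation of dialysis as its own outcome, using the item already derived from claims and CMS Form 2746.
- Show ventilation, feeding tube placement and CPR separately as well as combined.
- Reconcile the definition with the 29% in section 2.2, saying what that figure counts.

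The cost is a short edit to the endpoint definition and to the claims-extraction code list. No new data are needed.

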8.2 SAFETY AND OTHER ASSESSMENTS

SPIRIT is a one-time psychoeducational intervention. The study involves very low risk and the potential risk may include fatigue or emotional upset during the session.

Fatigue

As part of outcome assessment, HADS and PTSS-10 will be completed. Although these measures are not diagnostic tools, if a surrogate's HADS-Depression is high (≥ 15), the data collector will ask the surrogate if she/he is aware of the mood state and encourage to speak to his/her primary care provider. If a surrogate expresses suicidal ideation, the data collector will immediately notify the local site coordinator who will confer with the Site PI. This Site PI will determine if referral to the local mental health clinic (during hours) or the 24-hour Emergency Psychiatry Service (after hours) for evaluation of mental health or emergency intervention is necessary.

8.3 ADVERSE EVENTS AND SERIOUS ADVERSE EVENTS

8.3.1 DEFINITION OF ADVERSE EVENTS (AE)

SPIRIT is a one-time psychoeducational intervention. The study involves very low risk and the potential risk may include fatigue or emotional upset during the session, neither of which is a "medical occurrence". SPIRIT has been extensively tested in previous trials and no safety concerns have ever arisen. The present trial is to generate data to accelerate translation of the intervention into clinical practice.

8.3.2 DEFINITION OF SERIOUS ADVERSE EVENTS (SAE)

The trial targets ESRD patients on dialysis who already have serious life-threatening medical conditions and are likely to die within a year (by clinician's judgment). SPIRIT is an advance care planning intervention to prepare these patients and their surrogates for end-of-life decision making. SPIRIT's safety and beneficial effects (e.g., reducing psychological distress) have been consistently demonstrated. Participants' deaths or hospitalizations (or other events described above) during the trial are expected (and needed to answer the scientific questions) and will occur as part of the illness course. These events will not be considered as SAE in this trial. However, any participant's death will be reported to IRB through annual progress report and included in the NIH annual progress report.

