A new supplement study is a longitudinal cohort study leveraging the parent study. The objective is to assess the effect of the pandemic on the stability of end-of-life care preferences and on our key outcomes (dyad congruence on goals of care, patient decisional conflict, and surrogate decision-making confidence).

Aim 1. Compare the stability of patients' goals-of-care preferences over time, from pre-outbreak to during-outbreak, by group (SPIRIT vs control) and estimate effect by race (Blacks and Whites).

Aim 2. Assess the stability in the preparedness outcomes (dyad congruence, patient decisional conflict, and surrogate decision-making confidence) comparing pre-outbreak to during-outbreak by group, and estimate race effect.

Aim 3. Examine the associations of the COVID-19 Related Stress questionnaire, sex,

race/ethnicity, and other sociodemographic characteristics (e.g., education level, income) to change in the outcomes and the stability of patients' goals-of-care preferences after the COVID-19 outbreak.

Endpoints:

Primary Endpoints (Aim 1):

Dyad congruence on goals of care, patient decisional conflict, and surrogate decision-making confidence at 2 week post-intervention

Secondary Endpoints (Aim 3):

Surrogate HADS and PTSS scores at 3 months after the patient's death;

Exploratory (Aim 4):

EOL treatment intensity

Supplement Aim:

Dyad congruence on goals of care, patient decisional conflict, and surrogate decision-making confidence at 2-3 day post-intervention

Study Population:

400 patients and 400 surrogates of the patients participate as pairs (400 patient-surrogate dyads); adults (≥ 18 y); both genders; all race and ethnicity; ESRD/chronic dialysis population

For the supplement aims:

30 patients with ESRD + cognitive impairment, including early stages of dementia, who are not eligible for the parent study due to cognitive impairment, and 30 surrogates of the patients as pairs

Supplement cohort study:

~100 dyads who completed the baseline assessment and post-intervention assessment prior to the pandemic lockdown.

Phase:

Phase III effectiveness trial

For the supplement aims, NIH Stage 1 biobehavioral intervention research

**Description of
Sites/Facilities Enrolling
Participants:**

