7.3 LOST TO FOLLOW-UP

Patients lost to follow-up will not be applicable in this trial since all patients must come to the dialysis center for their treatment and thus can be contacted at the center.

A surrogate participant will be considered lost to follow-up if he or she fails to complete the scheduled 2-week follow-up (after the receipt of the intervention) and is unable to be contacted by the study site staff until the end of the 9-month follow-up period. Or, a surrogate participant will be considered lost to follow-up if he or she fails

to complete the scheduled 3-month follow-up (after the patient's death) and is unable to be contacted by the study site staff.

The following actions must be taken if a participant is determined to be lost to follow-up:

- The site will attempt to contact the participant and reschedule the missed appointment for 4 weeks and ascertain if the participant wishes to continue in the study.
- Before a participant is deemed lost to follow-up, the investigator or designee will make every effort to regain contact with the participant (where possible, 3 telephone calls and, if necessary, a certified letter to the participant's last known mailing address or local equivalent methods, or speak to the patient at the dialysis center). These contact attempts will be documented in the participant's record in REDCap.
- Should the participant continue to be unreachable, he or she will be considered to have withdrawn from the study with a primary reason of lost to follow-up.

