8.3.6 SERIOUS ADVERSE EVENT REPORTING

Not applicable.

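### The SAE exemption in section 8.3.2 is ambiguous for the 400 surrogates, and a serious surrogate event not classed as related to SPIRIT has no explicit recording or reporting route

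*Combined protocol and SAP*

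**What the plan says.** **Who is enrolled.** The synopsis gives "400 patients and 400 surrogates of the patients participate as pairs (400 patient-surrogate dyads"), and section 4.1 counts patients and "their surrogate decision-makers (total 800 individuals"). Section 7.3 applies the word participant to surrogates: "A surrogate participant will be considered lost to follow-up if he or she fails to complete the scheduled 2-week follow-up".

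**The exemption.** Section 8.3.2 opens with dialysis patients who are likely to die within a year. It then says of participants, not of patients, that their "deaths or hospitalizations (or other events described above) during the trial are expected (and needed to answer the scientific questions"). The same sentence closes by tying these events to the disease: "and will occur as part of the illness course". The consequence is: "These events will not be considered as SAE in this trial". The next sentence sends any participant's death to the IRB and NIH in annual progress reports. Section 8.3.5 repeats this.

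**What is switched off.** Severity (8.3.3.1), relationship to the intervention (8.3.3.2), the period of event assessment (8.3.4) and safety analyses (9.4.4) are all marked not applicable. So is the whole of "8.3.6 SERIOUS ADVERSE EVENT REPORTING".

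**What remains.** Section 8.3.5 tracks fatigue or emotional distress during the intervention session and reports aggregate counts to the DSMB. Sections 8.4.1 and 8.4.2 define unanticipated problems, including psychological harm to participants or others. They require notice to the IRB, NINR and DSMB within 24 hours, then a written SAE report. Section 8.2 adds: "If a surrogate expresses suicidal ideation, the data collector will immediately notify the local site coordinator who will confer with the Site PI". Section 10.1.6 has the DSMB review patient deaths and any adverse events twice a year.

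**The concern.** The argument for not treating death and hospitalization as SAEs is sound for patients on dialysis who were expected to be near the end of life. It has no force for their surrogates, who are enrolled as decision-makers and not because they are ill. Yet the operative sentence does not separate the two groups, and the SAE reporting section is empty.

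SPIRIT asks surrogates to prepare for life-or-death decisions, and Aim 3 measures their anxiety, depression and post-traumatic distress after bereavement. Section 8.2 foresees severe depression and suicidal ideation among them. The rare serious outcomes in this group are the ones that a DSMB would want to see in both arms. If nobody is told to record them, the trial cannot itself support a statement that SPIRIT is safe for surrogates.

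**Working it through.** No calculation applies beyond two sums: surrogates make up 400/800 = 50% of those enrolled, and the longest planned follow-up before any post-death survey is 9 + 12 = 21 months, for those who accept the extension. The rest is a matter of setting the sections side by side.

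**Step 1: does the answer depend on how the exemption is read?**
- Broad reading (all participants): a surrogate's death or hospitalization is excluded from being an SAE for a reason that does not fit surrogates.
- Narrow reading (patients only): the exclusion does not reach surrogates, but nothing else in 8.3 says what an SAE is for them, and 8.3.6 is not applicable.

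Either way, surrogates have no SAE definition.

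**Step 2: trace each type of surrogate event in the parent trial.**

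| Surrogate event | Route in the text | What is missing |
|---|---|---|
| Death | Annual reports to IRB and NIH (8.3.2, 8.3.5) | Not expedited; the DSMB list in 10.1.6 names only patient deaths |
| Suicide attempt or psychiatric admission, judged unexpected, related and a sign of greater risk | IRB, NINR and DSMB within 24 hours, then a written SAE report (8.4.1, 8.4.2) | Any method for judging relatedness (8.3.3.2); an SAE reporting procedure (8.3.6) |
| The same, not classed as related | None stated | Definition, ascertainment window, recording and reporting |
| Suicidal ideation voiced to a data collector | Site coordinator, then Site PI, who decides on referral (8.2) | Any instruction to record it as an event or notify the IRB or DSMB |

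**Step 3: check the 24-hour route for internal consistency.**
- 8.4.1 admits events that are only possibly related; 8.4.2 triggers the notice only for events that are related. The entry conditions differ.
- 8.4.2 needs a relatedness judgement; 8.3.3.2 says that relationship is not applicable.
- 8.4.2 promises a written SAE report; 8.3.6 says that SAE reporting is not applicable.

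**Step 4: can 8.3.5 fill the gap?** It covers only reactions during the intervention session. Control dyads have no session while enrolled: section 8.1 says that patient and surrogate participation will have ended before the delayed implementation is evaluated. Counts from 8.3.5 therefore cannot give a between-arm comparison.

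**Step 5: is ascertainment feasible?** The schedule in 1.3 has T1, T2, nine monthly check-in calls and a post-death contact at 3 months. Section 10.1.1.2 states that the monthly call is made to each member of the dyad. The schedule lists no monthly calls for the 12-month extension.

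**The case against.** The strongest reply is that the protocol is not silent. A reader might infer that a surrogate's suicide attempt, psychiatric admission or death has no route at all. The documents do not support that. Any participant's death is reported annually, and if participant includes surrogates in the exemption, it includes them in that sentence too. An unexpected, related harm goes out within 24 hours, psychological harm is expressly included, and 8.3.3.3 classes even in-session distress as unexpected, so the expectedness test would hardly block a report.

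A reader might also take it as settled that the exemption reaches all 400 surrogates. That is too strong. The section opens with dialysis patients, ties the events to the illness course, and is echoed in 8.3.5 as a rule about disease-related events. The evident intent is patients; the fault is that the wording does not say so.

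Nor is surrogate distress unmeasured. HADS and PTSS-10 are compared between arms after bereavement, a HADS-Depression score of 15 or more raises a REDCap flag (10.1.7), and the DSMB reviews any adverse events. The DSMB charter is not among the documents, so what the board sees by arm cannot be settled here.

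All of this stands, and it narrows the point. It does not close the gap for serious events that nobody has classed as related. Symptom scores at baseline and 3 months after a death are not a record of serious events, and a review of any adverse events depends on something upstream recording them.

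**Conclusion.** The point holds in a limited form. The scope of 8.3.2 is ambiguous for 50% of those enrolled, surrogate SAEs are undefined on either reading, and the only expedited route leans on two steps that other sections declare not applicable. As written, a surrogate's suicide attempt or psychiatric admission that is not classed as related has no explicit recording or reporting route in either arm.

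The number of events affected cannot be estimated: the documents give no surrogate event rate. It would be wrong to describe the gap as 21 months for every surrogate, since follow-up reaches that length only for dyads who agree to the extension. The conclusion assumes that no charter, manual or operating procedure outside these documents supplies the missing definition. It concerns safety data and consistency of wording; it does not touch the primary effectiveness analysis. It is a low-cost improvement that should be made.

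**What to change.** 1. In 8.3.2, limit the exemption to patients, and say what the reference to other events described above means.
2. Reconcile 8.3.3.2 and 8.3.6 with 8.4.1 and 8.4.2: state who judges relatedness and how, use one threshold for it in both 8.4 subsections, and replace the empty SAE reporting section with text that matches the written report in 8.4.2.
3. For surrogates in both arms, record death, suicide attempt and psychiatric hospitalization, whether or not thought related, at contacts already scheduled (T1, T2, the monthly calls and the 3-month post-death call). Report them by arm to the DSMB and to the IRB, and add surrogate deaths to the DSMB list in 10.1.6.
4. State how these events are ascertained during the 12-month extension, for which no calls are listed.

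Whether to add all-cause surrogate hospitalization or suicidal ideation is for the sponsor to decide. Clinical care of the surrogate stays with the existing pathway in 8.2.

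Cost: a protocol amendment, a short REDCap form and some additional reports, whose number the documents do not allow to be estimated. A fuller route is not foreign to this team: for the 30-dyad dementia supplement, 10.1.6 already sends adverse event information to the monitoring committee chair and notifies the IRB and NIH within one week.
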